To answer Aim 1B, transcription profiling by RNA-Seq will be performed on a subset of participants. Seven patients with greatest degree of coronary atherosclerosis vs. 7 patients with the least amount of coronary atherosclerosis and 7 patients with greatest degree of microbial translocation vs. 7 patients with the least amount of microbial translocation. Both groups will be matched by age and traditional cardiovascular risk factors. As Verdugo *et al* recently found that smoking can affect the monocyte transcriptome⁴², we will exclude patients who are active smokers in Aim 1B. Transcription profiling of monocytes by RNA-Seq will also be performed in a subset of 7 participants in the active teduglutide arm who have the greatest amount of coronary atherosclerosis before and after their teduglutide treatment in the Randomized Study of Teduglutide vs. Placebo.

[figure not shown]
To answer Aim 2, we propose a randomized, double-blind, placebo-controlled trial to assess the effects of treatment with teduglutide 0.05 mg/kg/day for 6 months duration compared to placebo. Recruitment for this interventional trial will occur concurrently with the cross-sectional study in Aim 1A. Participants who are recruited for the randomized study will complete Baseline Studies Part 1 and Part 2 as their baseline for the randomized study (see Figure 1a). Participants who are recruited for the neurological substudy will complete Visit A and B (see Figure 1b). *This design is intended to minimize risk of study procedures to patients by maximizing use of data and also to improve efficiency in recruitment.* Thus, the participants in the randomized study will also complete the cross-sectional study. These participants undergo the same baseline procedures again at the end of the 6-month intervention for their end-of-study procedures. We will refer to the procedures involved in the randomized study as the **Randomized Study of Teduglutide vs. Placebo.**

Figure 1a.

*Only for healthy controls and HIV+ subjects who will complete Baseline Study Part 2. Transcriptomic profiling (RNA-SEQ) will be performed on stored samples after the study has been completed.

Figure 1b.

[figure not shown]
III. Subject Selection

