1. Repeat all procedures performed at Visits 1, 2, 3 and 4 in four separate visits

Fecal occult blood testing at 1 year:

Participants who participated in the Randomized Study of Teduglutide vs. Placebo will be given the fecal immunochemical test kit to be performed at home at 1 year from the starting of study medication teduglutide or placebo. They will be asked to return this to the laboratory for processing. If the result returns abnormal, we would recommend follow-up with their primary care physician and also offer to the participant to perform a colonoscopy using study funds if their primary care physician agrees.

For Participants in Baseline Study Part 1 (Biomarkers, Immunology and Intestinal Permeability Studies) only:

All potential subjects will complete a brief telephone screen followed by a clinical evaluation to determine eligibility for the study. The first clinical evaluation will be performed in the Clinical Research Center (CRC) at Massachusetts General Hospital (MGH) during the screening visit. Written informed consent will be obtained from each subject upon arrival to the CRC during the first screen visit and prior to testing. The consent form will be discussed with the subject by a licensed investigator (MD or NP).

Visit 1:

- 1. Participant will meet with study investigator (M.D. or N.P.) to review the consent form and signing of informed consent
- 2. Detailed medical history, including assessment of history of anti-retroviral use, hepatitis status, nadir CD4 count, gastrointestinal disease, prior history of CNS opportunistic infections and risk factors for cardiovascular disease, including smoking history, family history, and history of recreational drug use
- 3. Physical examination
- 4. Fasting blood will be obtained for glucose, comprehensive metabolic panel, CBC plus differential, high-sensitivity C-reactive protein, insulin, hemoglobin A1C, lipids, T-cell subset, and HIV RNA (for HIV-infected patients) and HIV ELISA test (for HIV-negative controls). Additional blood will be collected for isolation of peripheral blood mononuclear cells for immunological studies, serum and plasma to be frozen and stored.

Visit 2:

- 1. Intestinal Permeability Study (sugar probe solution drink and urine collection)
- 2. Twenty-six milliliters of blood (3 ACD tubes) will be collected for isolation of peripheral blood monocytes.
- 3. Bionutrition:
 - -Anthropometry (weight, height, waist and hip circumference measurements)

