Statistical Analysis Plan: For the primary outcome assessment, intention to treat principle will be applied in the analysis of this randomized placebo-controlled trial. For analysis of our primary outcome of arterial inflammation, we will compare the mean changes in arterial inflammation as assessed by FDG-PET measured as target to background ratio (TBR) of standardized uptake value in the group is randomized to teduglutide to the group that is randomized to placebo using independent samples t-test. Secondarily, we will also examine whether or not the mean of within group changes during the intervention period is zero using paired sample t-test. For secondary endpoints including change in markers of intestinal permeability, innate immune activation and microbial translocation, we will use the independent samples t-test to compare the means of the changes between the teduglutide group and the placebo group. In addition, longitudinal linear mixed effects modeling will be applied. The model will include random subject level intercept, fixed discrete time and group, and time \times group interaction term to characterize the within-group longitudinal means and to compare the between group difference in those longitudinal means. Effects of the potential confounders, (lipids, age, gender, smoking, diabetes mellitus, hypertension and other cardiovascular risk factors that may be different between the groups), will be adjusted by including them in the model as the covariates. We will utilize all available observations for this modeling even if there are some patients who have missing data at any time. If necessary, we will also perform Markov Chain Monte-Carlo (MCMC) based multiple imputation procedure.

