Sample Size Determination: With 30 patients in each group and up to 10% attrition (i.e. evaluable n=27/group), this trial can detect at least a between group difference of 0.2244 in the two within person TBR mean changes at a 5% significance level with 85% power by a two-sided independent samples t-test. This assumed that the standard deviation of the within subject TBR change is 0.27, which was estimated from our prior study at MGH study of similar patient population²⁸ of which the observed mean \pm (standard deviation) of the cross sectional TBR data was 2.24 (\pm 0.35) and the assumed pre- to post intervention longitudinal correlation was 0.7. This detectable effect size is close to 10% of the baseline mean 2.24, and we anticipate that the placebo group will show no change (or even increase its mean value). The effect size of 10% is of clinical significance as it is similar to the amount of decrease seen with statin treatment for 3 months⁵⁹, the most effective medical therapy we have to date for treatment of atherosclerotic disease and prevention of MI.

VII. Risks and Discomforts

Colonoscopy: Colonoscopy are generally safe procedures and complications are rare. Given the underlying HIV infection of the study participants, there is potential for the sequellae of the endoscopy complications outlined below to be more serious and more difficult to treat.

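### The primary TBR test leaves out baseline TBR and so gives up precision, and the plan does not say which method governs when a month-6 scan is missing

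*Combined protocol and SAP*

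**What the plan says.** **Primary analysis.** The Statistical Analysis Plan for the randomized study (Aim 2) opens: "For the primary outcome assessment, intention to treat principle will be applied in the analysis of this randomized placebo-controlled trial". Mean TBR change is then compared "in the group is randomized to teduglutide to the group that is randomized to placebo using independent samples t-test". No covariate enters this test.

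**Other methods.** After a sentence on secondary endpoints, the same paragraph adds a longitudinal mixed model with a random intercept, time, group and their interaction, adjusted for cardiovascular risk factors. Baseline TBR is not among the listed covariates. Of this model the plan says: "We will utilize all available observations for this modeling even if there are some patients who have missing data at any time". It then adds: "If necessary, we will also perform Markov Chain Monte-Carlo (MCMC) based multiple imputation procedure". Neither method is tied to the primary TBR result. No trigger for imputation, imputation model or missing-data assumption is given.

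**Sample size (Aim 2).** The test is sized as "With 30 patients in each group and up to 10% attrition (i.e. evaluable n=27/group", for a difference of 0.2244 with change SD 0.27, two-sided 5% and 85% power. The SD is built from a cross-sectional SD of 0.35, and "the assumed pre- to post intervention longitudinal correlation was 0.7".

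**Month 6.** The research design for Aim 2 says: "These participants undergo the same baseline procedures again at the end of the 6-month intervention for their end-of-study procedures". Section V lists for the final visits: "Repeat all procedures performed at Visits 1, 2, 3 and 4 in four separate visits". Section VII plans an end-of-study colonoscopy for all interventional participants. None of these places mentions people who have stopped study drug.

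**Stopping.** Section IX removes participants from the study for listed events. For intolerable side effects it says only that they may be discontinued, without saying from what. The pregnancy paragraph in Section VII stops the drug and rules out radiologic procedures.

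**The concern.** Baseline TBR is scheduled for every randomized participant, and the plan expects it to predict month-6 TBR strongly. A change score fixes the weight on baseline at 1, whereas the plan's own assumptions imply a slope of 0.7. The excess weight adds noise, and it carries part of any chance baseline imbalance into the result. In a trial of 60 that loss is worth avoiding, because recovering it needs no extra data.

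The second issue is what happens when a month-6 scan is missing. A change needs both PET scans, and the sample size is stated for evaluable participants. If scans are missing for reasons linked to both arm and outcome, a t-test on those with both scans need not estimate the effect of assignment. The plan holds methods that could deal with this, but it does not say which one decides the primary result. Two analyses could therefore disagree with no rule for choosing between them.

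**Working it through.** **Inputs** (Sample Size Determination, Aim 2): SD 0.35 at one time point, correlation r = 0.7, change SD 0.27, difference 0.2244, 30 per arm, 27 evaluable, two-sided 5%. Equal SDs before and after are assumed, as the plan's change SD implies.

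**1. The plan's own figure.**
- Change SD = 0.35 × √(2 × (1 − 0.7)) = 0.271, which the plan gives as 0.27.
- Noncentral-t power for 0.2244 with SD 0.27, n = 27 per arm, 52 df: 85.0%. The stated figure reproduces. With the unrounded SD it is 84.7%.
- With all 30 per arm scanned, power would be 88.6%. The plan's 85% therefore already allows for the loss of 3 per arm.

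**2. Adjusting for baseline.**
- ANCOVA residual SD = 0.35 × √(1 − 0.7²) = 0.250.
- Variance ratio to the change score = (1 + r)/2 = 0.85. Estimating the slope costs a factor of about 1 + 1/(54 − 4) = 1.02, so the ratio in practice is about 0.87.
- Power at 27 per arm: 89.9% (noncentral t, 51 df) and 89.4% by simulation.
- Detectable difference at 85% power: 0.208 instead of 0.2244.

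**3. Participants saved.** ANCOVA power is 84.5% at 23 per arm and 86.1% at 24 by formula. By simulation it is 84.0% and 85.5%. Matching 85% takes 24 per arm, a saving of 27 − 24 = 3.

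**4. Sensitivity to the assumed correlation** (SD 0.35 held, 27 per arm).

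| r | change-score t-test | ANCOVA |
|---|---|---|
| 0.5 | 63.8% | 76.1% |
| 0.6 | 73.4% | 82.4% |
| 0.7 | 84.7% | 89.9% |
| 0.8 | 95.5% | 97.1% |

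**5. Chance imbalance.** The SE of the baseline difference is 0.35 × √(2/27) = 0.095. An imbalance of one SE shifts the change-score contrast by (1 − 0.7) × 0.095 = 0.029, about 13% of 0.2244.

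**6. Does the mixed model already adjust?** No. TBR has two visits, and the model has free group, time and interaction terms. With complete data its fitted means are the four cell means, so the interaction equals the difference in mean changes. A fit to simulated complete data agreed: −0.2034 for both the interaction and the difference in mean changes, against −0.1953 for ANCOVA.

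**7. Missing scans, illustration only.** The documents give no stopping rate by arm. Assume no true effect, complete placebo data, k of 30 teduglutide scans missing, and those missing worse by δ. Bias = (k/30) × δ, and SE = 0.27 × √(1/(30 − k) + 1/30).

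| δ | k | bias | t-test type I error |
|---|---|---|---|
| 0.27 | 3 | 0.027 | 6.6% |
| 0.27 | 6 | 0.054 | 11.1% |
| 0.135 | 3 | 0.0135 | 5.4% |
| 0.135 | 6 | 0.027 | 6.5% |

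With equal missingness and the same δ in both arms, type I error stays at about 5%. ANCOVA alone does not remove the bias: its type I error is 6.6% and 12.0% in the first two rows.

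**The case against.** **The t-test is valid and meets its stated power, so ANCOVA is a preference.** The first half stands: there is no validity error and the trial is not undersized on its own assumptions. But the gain follows from those same assumptions, and it is larger if 0.7 proves optimistic.

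**The plan already handles missing data.** This partly stands. The mixed model uses all available observations, imputation is allowed for, participants are compared by assigned group, and 10% attrition is declared openly. A reader might infer that the intention-to-treat label is empty and the primary result biased. The documents do not support that. They leave open which method governs. The illustration needs loss in one arm only, and the 11.1% needs twice the planned attrition as well. Section IV also provides for a dose reduction when gastrointestinal side effects occur, so such effects need not end participation.

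**Follow-up after stopping drug is settled.** This also partly stands. For the events listed in Section IX, removal from the study points to no month-6 scan. Section VII is explicit that pregnancy rules out imaging, so the two sections agree on that case. A reader might infer that any stopping of drug ends follow-up, but the wording on intolerable side effects does not say so. Text directly before the statistical section was not available to us, so silence on this point carries that caveat.

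**Baseline TBR may not be complete.** Fair. Section V places randomization before the visit that holds the baseline PET, while Section III has baseline completed before entry. Baseline TBR is scheduled for everyone, but not guaranteed.

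**Conclusion.** The point holds as one about precision, with a secondary gap in specification. On the plan's inputs, baseline adjustment raises power from 85% to about 89-90% at 27 per arm. This rests on r = 0.7 and equal SDs before and after. From 27 × 0.85 = 22.95 a reader might infer a saving of 4 per arm, more than the expected loss. That does not hold, because 23 per arm falls short of 85%. The saving is about 3, equal to the expected loss.

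On missing scans, the defect is that no method is named for the primary result. Neither the size nor the direction of any bias can be derived from the documents. The change is worth making, but the trial does not fail without it.

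**What to change.** 1. **Primary analysis.** Make it an ANCOVA of month-6 TBR on baseline TBR and assigned arm. Keep the change-score t-test as a sensitivity analysis, labelled as restricted to participants with both scans. This needs no new data and no change in sample size. It should be fixed before outcomes are seen by arm.
2. **Missing TBR.** State which of the methods already in the plan (mixed model or multiple imputation) governs the primary result when month-6 TBR is missing, and under what assumption. Add a delta-adjusted or reference-based sensitivity analysis, and report missing scans with reasons by arm. The cost is a few sentences and modest analysis work.
3. **Follow-up.** Reconcile the month-6 visits in Section V, the teduglutide and pregnancy paragraphs in Section VII and the discontinuation paragraph in Section IX, so that it is clear whether someone who stops study drug stays in the study for the month-6 assessments. Which rule applies is for the investigators to decide, and this review does not propose one. The cost is wording.

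### The primary TBR comparison is an unadjusted t-test on change scores; adjusting for the baseline TBR already collected would cut the variance by 15% at the plan's own correlation and raise power from 85% to about 89–90%.

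*Combined protocol and SAP*

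**What the plan says.** The Statistical Analysis Plan for the Randomized Study of Teduglutide vs. Placebo (Aim 2) takes change in TBR as the primary outcome. It compares mean change "in the group is randomized to teduglutide to the group that is randomized to placebo using independent samples t-test". No covariate enters this test. The same t-test on changes is planned for the secondary markers of permeability, immune activation and microbial translocation.

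The Aim 2 Sample Size Determination is built on that test. It states that "this trial can detect at least a between group difference of 0.2244 in the two within person TBR mean changes". The power claimed for this is 85%, with a two-sided error rate of 5%. The inputs are 27 evaluable per arm and the assumption that "the standard deviation of the within subject TBR change is 0.27". That SD comes from a cross-sectional SD of 0.35, and "the assumed pre- to post intervention longitudinal correlation was 0.7".

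The SAP then adds a longitudinal mixed model: "The model will include random subject level intercept, fixed discrete time and group, and time"-by-group interaction. Its covariates are lipids, age, gender, smoking, diabetes, hypertension and "other cardiovascular risk factors that may be different between the groups". Baseline TBR is not on the list.

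Baseline TBR is nevertheless available. FDG-PET/CT is part of Visit 4, the baseline studies serve as the randomised trial's baseline (Subject Selection, overview), and the procedures are repeated at month 6.

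**The concern.** A change score subtracts the whole of the baseline value, which amounts to fixing the regression slope of follow-up on baseline at 1. When the two measurements have equal variance, the slope that minimises residual variance is the correlation, here 0.7. The change-score comparison therefore carries avoidable noise. In any one trial it also passes part of a chance baseline difference between the arms into the treatment estimate.

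What is at stake is power in a small trial with a burdensome protocol: each randomised participant has two colonoscopies and two FDG-PET/CT scans. The plan's power also depends heavily on a correlation that was assumed rather than estimated, and the change-score test is the more sensitive of the two analyses to that assumption.

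**Working it through.** **Inputs** (Aim 2 Sample Size Determination): cross-sectional SD σ = 0.35; correlation ρ = 0.7; 30 × 0.9 = 27 evaluable per arm; difference 0.2244; two-sided α = 0.05. Baseline and month-6 SDs are taken as equal, which the plan's own figure of 0.27 implies.

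**1. Reproduce the plan.**
- SD of change = σ√(2(1−ρ)) = 0.35 × √0.6 = 0.2711, rounded in the plan to 0.27.
- Noncentral-t power with 52 df and SD 0.27 is 85.0%, and the difference detectable at 85% power is 0.2244. Both stated figures are confirmed.
- With the unrounded SD of 0.2711, power is 84.7% and the detectable difference is 0.225.

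**2. Adjust for baseline.**
- Residual SD = σ√(1−ρ²) = 0.35 × √0.51 = 0.2499.
- Variance ratio = (1−ρ²) / (2(1−ρ)) = (1+ρ)/2 = 0.85. The variance falls by 15% and the SD by about 8%.
- Noncentral-t power with 51 df is 89.9%. Inflating the residual variance by 1/51 for chance baseline imbalance gives 89.3%. Starting from the rounded 0.27, the two figures are 90.1% and 89.6%.
- Simulation of 20,000 trials with the unrounded SD gave 84.4% for the t-test and 89.2% for the adjusted analysis. A separate run scaled to the rounded SD gave 85.4% and 89.6%.
- The difference detectable at 85% power falls from 0.225 to 0.208.
- The t-test needs 31 per arm to reach 89.4% and 32 to reach 90.3%.

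**3. Vary the correlation**, holding σ = 0.35, 27 per arm and the difference at 0.2244:

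| ρ | Variance ratio | Change-score t-test | Baseline-adjusted | Adjusted, with imbalance allowance |
|---|---|---|---|---|
| 0.5 | 0.75 | 63.8% | 76.1% | 75.3% |
| 0.6 | 0.80 | 73.4% | 82.4% | 81.6% |
| 0.7 | 0.85 | 84.7% | 89.9% | 89.3% |
| 0.8 | 0.90 | 95.5% | 97.1% | 96.8% |

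**4. Chance baseline imbalance.**
- The SD of the between-arm difference in mean baseline TBR is 0.35 × √(2/27) = 0.095.
- At ρ = 0.7, a one-SD imbalance shifts the expected change-score contrast by (1−0.7) × 0.095 = 0.029, about 13% of 0.2244.
- The standard error of that contrast is 0.2711 × √(2/27) = 0.074, so the shift is 0.39 standard errors. Since 0.39² ≈ 0.15, this is the same 15% of variance seen from another side.

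**5. Does the mixed model recover the loss?** TBR is measured at two times. The model has baseline in the response, a random intercept and a free group effect, so in complete data its time-by-group term is the difference in mean changes. Time-fixed covariates entered as main effects describe level, not change, and drop out of that term. A simulated fit gave an estimate of −0.1139 and a standard error of 0.0617 both with and without covariates, equal to the change-score contrast.

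**The case against.** The strongest reply is that this is a preference for efficiency and not a defect. Under randomisation the change-score t-test is unbiased and holds its type I error. The plan's test, SD and power agree with one another, and a proof-of-concept trial with 85% power is adequately sized. All of that stands, and it limits the weight of the point.

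Several narrower objections also have force:

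- **The correlation could be higher than 0.7.** The documents do not show which way the assumption errs. At 0.8 the gain is only 1 to 2 percentage points.
- **Chance imbalance is not a second harm.** Step 4 shows that it is the same variance and should be counted once.
- **The mixed-model equivalence has conditions.** It needs complete data and time-fixed covariates. The plan allows for up to 10% attrition and uses all available observations, and lipids are measured again at month 6, so the fitted term could differ somewhat from the raw contrast. Neither feature turns it into a baseline-adjusted analysis. The text also leaves it unclear whether this model covers TBR at all.
- **The secondary markers are unquantified.** The documents give no SDs or correlations for them, so the 15% figure applies to TBR only.
- **The open-ended covariate list is a separate matter.** It is a prespecification weakness of the additional model and has no bearing on the primary test's power.

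None of these alters the result at the plan's own inputs.

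**Conclusion.** The concern holds as a recommended improvement; it is not an error. At the plan's assumed correlation, adjusting for baseline TBR removes 15% of the variance and lifts power from 85% to about 89–90%, equivalent to 4 or 5 more evaluable participants per arm under the t-test. The size rests on the plan's SD of 0.35, equal SDs before and after treatment, and a correlation of 0.7. With equal SDs, the large-sample variance of the adjusted estimate is never greater than that of the change score. The gain is largest when the correlation is below the assumed value, which is where the planned test loses most power.

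**What to change.** - Make the primary analysis an analysis of covariance of month-6 TBR on randomised arm with baseline TBR as a covariate. Keep the t-test on change as a sensitivity analysis.
- Analyse each secondary marker in the same way, using its own baseline.
- In the mixed model, either constrain the arms to a common baseline mean, or take baseline out of the response and enter it as a covariate. Adding baseline as a covariate while it also remains in the response achieves nothing in complete data. State whether the model applies to TBR.
- Replace the covariates chosen by between-group difference with a short list fixed before unblinding.
- Update the Aim 2 Sample Size Determination to name the new test. The existing 85% can stay as a conservative figure, or the adjusted power can be given with a range of correlations on both sides of 0.7.

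The cost is wording in the two Aim 2 paragraphs and one degree of freedom. No additional data, visits or participants are needed.

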Medical Record Review: Medical records will be reviewed for relevant clinical data for subjects who are currently followed at MGH or BWH for clinical care. Subjects who receive clinical care from external providers will be asked to sign a Release of Information form. We will request and/or review relevant medical history, laboratory results and treatment history for HIV and/or Hepatitis B and C.

Visit 3 (Colonoscopy)

- 1. Colonoscopy will be performed in the MGH GI endoscopy suite and performed according to standard MGH clinical colonoscopy protocol.
- 2. Blood draw for isolation of cells to be used for immunological studies.

Follow-up Phone call:

The study coordinator or a study investigator will have a follow up phone call with subjects the day after the colonoscopy procedure. The purpose of the call will be to assess how the participant tolerated the procedures and whether an adverse event occurred. If an adverse event occurred, a study physician will speak with the participant. If a study coordinator calls the subject, she/he will inform the subject during the call that a study doctor will call them if they wish.

If eligible, subject will be randomized to either teduglutide or placebo and return for:

Visit 4 (Baseline visit):

- 1. Meet with investigator for dispensing of study drug (including administration of first dose and 30 minute observation)
- 2. Serum HCG will be obtained STAT as a pregnancy test for women prior to FDG-PET
- 3. Blood drawing for RNA-sequencing, and for sera and plasma to be frozen for assays to be run in batch using kits.
- 4. FDG-PET/CT
- 5. Neurocognitive Test Battery administered between 18F-FDG tracer injection and prior to FDG PET/CT scan.
- 6. Center for Epidemiological Studies-Depression Scale (CES-D).
- 7. Cognitive Function Instrument (CFI), and Patient's Assessment of Own Functioning Inventory (PAOFI) Questionnaire.

Visit 4 may be conducted before Visit 3, depending on scheduling availability.

Follow up safety visit 1 month after randomization and then at month 3:

- 1. Blood draw for safety labs, comprehensive metabolic panel, amylase, lipase, CBC with differential, and blood samples will also be stored for biomarkers to be run in batch (sCD14, LPS, I-FABP, sCD163)
- 2. Assess for side effects
- 3. Assess for change in medical problems or medications
- 4. Urine HCG for women
- 5. PAOFI and CES-D at month 3

Final visits at month 6:

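### The supplementary mixed model names only a random intercept; for the four markers measured at four visits, its test of baseline-to-month-6 change could run at roughly 5.5–14% instead of 5%

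*Combined protocol and SAP*

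**What the plan says.** The Statistical Analysis Plan for the Randomized Study of Teduglutide vs. Placebo (Aim 2) gives two analyses for the secondary markers. The first is a t-test on change: "we will use the independent samples t-test to compare the means of the changes between the teduglutide group and the placebo group". The second is supplementary: "In addition, longitudinal linear mixed effects modeling will be applied". Of that model the plan says "The model will include random subject level intercept, fixed discrete time and group", with a time-by-group interaction. Its stated purpose is to describe the within-group means over time and "to compare the between group difference in those longitudinal means". The plan names no random slope, residual correlation structure, unstructured covariance or robust standard error, and does not say which interaction contrast will be tested.

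The visit schedule is in section V, Study Procedures. There is a "Follow up safety visit 1 month after randomization and then at month 3", at which "blood samples will also be stored for biomarkers to be run in batch (sCD14, LPS, I-FABP, sCD163" and so on. For the month-6 visits the instruction is "Repeat all procedures performed at Visits 1, 2, 3 and 4 in four separate visits". These four markers therefore have values at months 0, 1, 3 and 6. TBR from FDG-PET and sugar-probe permeability are measured only at baseline and month 6.

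**The concern.** A model whose only within-subject term is a random intercept, with independent residuals, gives every pair of visits the same correlation. Samples taken one month apart are usually more alike than samples taken six months apart. The model pools all six pairs of visits to estimate within-subject variability. Months 0 and 6 are the most distant pair, so the pooled value understates the variance of the change between them.

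The secondary endpoints are defined as changes in markers, so the month-6 interaction coefficient is a natural one to report from this model. The same model carries the covariate adjustment and uses participants with incomplete data, so it may well be cited. A standard error that is too small would make a claim that teduglutide altered translocation or monocyte activation easier to reach than the nominal 5% implies.

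**Working it through.** **The plan's own figure.** The Sample Size Determination for Aim 2 concerns TBR only. SD of change = 0.35 × √(2 × (1 − 0.7)) = 0.271, which the plan gives as 0.27. With 27 per arm and a two-sided 5% t-test, a difference of 0.2244 has 85.0% power (noncentral t). The figure reproduces. The plan states no error rate for the mixed model, and the 0.7 is an assumption for TBR, not for any plasma marker.

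**Inputs from the documents.** Visits at 0, 1, 3 and 6 months; a random intercept; and, for arm size, "With 30 patients in each group and up to 10% attrition (i.e. evaluable n=27/group".

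**Assumed inputs.** Equal variance at each visit, and the correlation patterns below.

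**Formula.** With complete data and common variance s²:
- true variance of the 0-to-6 change = 2s²(1 − r₀₆), where r₀₆ is the correlation between months 0 and 6;
- variance the random-intercept model estimates = 2s²(1 − r̄), where r̄ is the mean of the six pairwise correlations;
- ratio Q = (1 − r₀₆)/(1 − r̄), and actual type I error ≈ 2Φ(−1.96/√Q).

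**Example: decay of 0.90 per month, no measurement error.** The lags are 1, 3, 6, 2, 5 and 3 months, with correlations 0.900, 0.729, 0.531, 0.810, 0.590 and 0.729, so r̄ = 0.715. Q = (1 − 0.531)/(1 − 0.715) = 1.644 and √Q = 1.282. Type I error = 2Φ(−1.529) = 12.6%.

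**Example: the same decay with measurement error.** Variance shares are stable 0.5, serial 0.3 and noise 0.2. Then r̄ = 0.5 + 0.3 × 0.715 = 0.7145 and r₀₆ = 0.5 + 0.3 × 0.531 = 0.659. Q = 0.341/0.2855 = 1.193, and type I error = 7.3%.

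| Assumed pattern | r₀₆ | r̄ | Q | SE too small by | Type I error |
|---|---|---|---|---|---|
| Equal correlation 0.7 | 0.70 | 0.70 | 1.00 | 0% | 5.0% |
| Decay 0.80 per month | 0.26 | 0.51 | 1.50 | 18% | 11.0% |
| Decay 0.90 per month | 0.53 | 0.72 | 1.64 | 22% | 12.6% |
| Decay 0.97 per month | 0.83 | 0.90 | 1.75 | 24% | 13.9% |
| Serial 0.8, noise 0.2, decay 0.90 | 0.43 | 0.57 | 1.34 | 14% | 9.1% |
| Stable 0.5, serial 0.3, noise 0.2, decay 0.90 | 0.66 | 0.71 | 1.19 | 8% | 7.3% |
| Stable 0.6, serial 0.1, noise 0.3, decay 0.90 | 0.65 | 0.67 | 1.06 | 3% | 5.6% |
| Linear fall 0.80 to 0.70 | 0.70 | 0.75 | 1.22 | 9% | 7.6% |
| Linear fall 0.75 to 0.70 | 0.70 | 0.73 | 1.10 | 4–5% | 6.1% |

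Adding a stable component without noise changes nothing. It multiplies both 1 − r₀₆ and 1 − r̄ by the same factor, so Q is the same as for pure decay. Independent noise is what lowers the figure.

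**Simulation.** With 27 per arm, no treatment effect and 20,000 trials per pattern, the change contrast agreed with the formula (for example 12.4% for calendar decay with r₀₆ = 0.5, formula 12.5%). REML fits with 30 per arm and 10% dropout (3,000 trials) gave 11.2–14.1% under three noise-free decay patterns and 5.6% under equal correlation.

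**Other targets, same balanced simulations:**
- month-6 level difference: 5.0–5.5%;
- global time-by-group F test: 4.9–7.5%;
- month-1 change when correlation falls: 0.04–4.0% (conservative);
- t-test on baseline-to-month-6 change: 4.7–5.4%;
- change in a two-visit outcome: 4.9–5.1%.

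**The case against.** The strongest reply is that a valid test of the same question is already planned and named first. The t-test on change holds its level in every pattern tried, and the mixed model comes only in addition. That stands, and it limits the consequence.

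Three further objections also stand:
- The plan says what the model will include, not that nothing else will be included. Serial residuals or robust standard errors would be compatible with the text. So this is under-specification that becomes a fault if the model is fitted as literally described, rather than a stated choice of equal correlation.
- The plan does not name the month-6 change as the mixed-model contrast. That contrast is a natural reading because the endpoints are changes, but it is not the only one.
- These are plasma assays, so some measurement noise is expected, which pulls the error rate toward the lower part of the range.

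A reader might infer that the false-positive rate is 11–14% whenever correlation falls with time, or that every month-6 between-arm standard error is too small. The documents support neither. The first requires fairly persistent serial correlation with little measurement error, and no marker correlation is given. The second fails because the month-6 level difference is not inflated.

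What the reply does not remove is that two analyses of the same change are prespecified, one may be anticonservative, and no rule says which governs if they disagree.

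**Conclusion.** The point holds as a minor one, confined to a supplementary analysis of four secondary markers. Fitted as written, the random-intercept model understates the standard error of the between-arm difference in baseline-to-month-6 change if correlation falls with lag and variances are equal across visits. The direction follows from the algebra; the size depends on correlations that the documents do not give. Across the assumptions examined, the nominal 5% test runs at roughly 5.5–14%, with the upper part (11–14%) requiring serial decay without measurement error and about 5.5–9% applying with 20–30% independent noise. The global interaction test is affected only slightly, up to about 7.5%. It should not be inferred that the primary TBR result or sugar-probe permeability is at risk: with two visits there is only one correlation, so the equal-correlation assumption imposes nothing.

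**What to change.** For sCD14, LPS, I-FABP and sCD163, state in the Aim 2 Statistical Analysis Plan that the mixed-model test is the time-by-group contrast for baseline-to-month-6 change. Replace the random-intercept structure with an unstructured within-subject covariance over the four visits, using Kenward-Roger degrees of freedom. With complete data and no covariates this contrast reduces to the t-test on change, which holds its level. If the unstructured model does not converge, keep the random intercept and use cluster-robust standard errors with a small-sample correction.

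The cost is SAP wording, ten covariance parameters (4 × 5/2) instead of two, and a slight loss of power if equal correlation does hold. No change to visits, sampling or sample size is needed.
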